16.	APP	PENDIX 3 - FLOW DIAGRAM OF STUDY DESIGN	48
17.	APP	PENDIX 4 – SUMMARY OF PROTOCOL AMENDMENTS	49
		PENDIX 5 – FLOW DIAGRAM FOR COVID-19 CHANGE TO REFERRAL AND ING PROCESS	51

Not for Public Circulation or Reproduction

1. Overview

Title of study

SALTS: A parallel, two-arm, randomised controlled trial to determine the effects of a 12-week dietary salt reduction intervention (Saltswitch app + dietary salt substitute) on urinary sodium excretion in adults with high BP.

Investigators and study centres

This study is being designed and conducted at the National Institute for Health Innovation (University of Auckland). The Principal Investigator is [name]. The Co-investigators are [name] [name], [name], and [name] [name].

Study period

May 2019 to 31 March 2022. It is anticipated that participant recruitment will begin in May 2019.

Clinical phase

SALTS is a phase III randomised controlled trial (RCT).

Objectives

The primary objective of this study is to determine the effects of a 12-week dietary salt reduction intervention (SaltSwitch app + dietary salt substitute) on urinary sodium excretion in adults with high BP.

The secondary objectives are to determine the effects of the dietary salt reduction intervention on: (1) urinary potassium excretion (week 12), (2) systolic blood pressure at week 12 (3) sodium content of packaged food purchases (weeks 11 & 12), (4) the number of participants achieving BP control (≤135/85 mmHg; week 12), and (5) use and acceptability of the SaltSwitch app and dietary salt substitute (week 12).

Additional objectives are to record serious adverse events, and if the intervention is found to be effective then cost-effectiveness and cost-utility analyses will also be completed.

Duration of treatment

12 weeks (preceded by a 2-week baseline phase).

Study design and methodology

SALTS is a 14-week, two-arm, parallel randomised controlled trial. A two-week baseline period (weeks -2 to -1) will be followed by 12 weeks intervention (weeks 1 to 12) Three hundred and twenty six adults (163 per group) with high BP will be randomised in a 1:1 ratio to receive either the salt reduction intervention (SaltSwitch app + dietary salt substitute) or control (generic information about heart-healthy eating), stratified by ethnicity (Māori and non-Māori) and age (<55yrs and 55yrs+). Randomisation will take place at the end of the baseline phase (beginning of week 1). The primary outcome is 24-hour urinary sodium excretion (mg/day) estimated using a spot (casual) urine sample at week 12. Secondary outcomes are (1) urinary potassium excretion (week 12), (2) average systolic BP (week 12),

Not for Public Circulation or Reproduction

(3) sodium content per 100g of packaged food purchases (week 12), (4) the number of participants achieving BP control (<135/85 mmHg; week 12)[1], and (5) use and acceptability of the SaltSwitch app and dietary salt substitute (week 12). Serious adverse events will be recorded, and if the intervention is effective then cost-effectiveness and cost-utility analyses will also be completed. Both groups will complete home-based BP measures twice per day (morning and evening) in triplicate during weeks -1, 6 and 12; collect a spot (casual) urine sample at weeks -1 and 12; and scan barcodes of all packaged foods purchased for consumption in the home during the 2-week baseline, and during the 2 weeks at the end of intervention (weeks 11 and 12) using a tailored study smartphone application.

Study population and number of participants

Participants will be 326 free-living adults (18yrs+) with high BP who own a smartphone and are willing to do grocery shopping during the study period. A General Practitioner (GP), healthcare provider, or study staff will have confirmed that they have high BP, and \geq 80% will have a recorded systolic BP (SBP) of \geq 140 mmHg at screening. Individuals with high BP and on antihypertensive medication will be eligible since effects of dietary salt reduction are additional to drug therapy[2]. The majority of participants (\geq 70%) will reside in the Auckland region.

Recruitment will be undertaken using four main methods: (1) face-to-face recruitment with a stand to promote the study and offer BP checks for interested participants. This recruitment approach will take place at Green Cross pharmacies, shopping malls, local events and markets, and the Stroke Foundation blood pressure van, (2) at Green Cross GP practices and other primary care providers NIHI has established relationships with e.g. the Fono. (3) using Social Media e.g. advertisements on Facebook to encourage people to register their interest and attend screening clinics at Grafton Campus, (4) via market research panels where a survey is sent to the panel and those who are interested can complete some questions about their eligibility and supply contact details, they are then invited to attend a screening clinic at Grafton Campus. Prospective participants can also obtain measurements required for screening from their local health professional. The health professional must record, sign and date a copy for the individual to send an electronic version to study staff by email to assess and if eligible, complete a referral form. Leaders of Māori communities NIHI has existing relationships with may also be approached to increase recruitment of Māori. Recruitment will be targeted to Auckland regions with higher proportions of Māori and lowincome residents but may be expanded to include other regions of New Zealand, if required to meet the recruitment target.

Main criteria for inclusion

Participants will be eligible if they:

- Are aged 18 years or older
- Own a smartphone (iPhone or Android)
- Have a seated SBP of 140-200 mmHg and/or diastolic BP (DBP) of 85-120 mmHg at screening
- Are willing to do grocery shopping during the study period
- Can read and understand English
- Can provide informed consent

Exclusion criteria

Participants will be excluded if they:

Currently use a dietary salt substitute

Not for Public Circulation or Reproduction

- Currently use the FoodSwitch app
- Have a contraindication to changing dietary sodium or potassium intake e.g. severe kidney disease or use a potassium sparing diuretic
- Are taking medication that may lead to hyponatraemia or acute build-up of body water such as furosemide, regular NSAID use, or regular prednisone use
- Have had a stroke or cardiovascular event (hospitalisation for heart attack, coronary artery revascularisation (CABG or stenting), stroke or heart failure) in the previous 6 months
- Have diagnosed heart failure

Eligible participants must provide at least six home-based BP measures during the two-week baseline period (weeks -2 and -1+/- two weeks),) and return a spot (casual) urine sample at baseline (week -1+/- two weeks).

Reference therapy

Dietary advice available from the Heart Foundation of NZ.

Criteria for evaluation

Primary outcome

24-hour urinary sodium excretion (mg per day) estimated using a spot (casual) urine sample at week 12.

Secondary outcomes

- 1. Urinary potassium excretion (mg per day) at week 12
- 2. Average systolic BP at week 12
- 3. Sodium content (mg per 100g) of packaged food purchases (weeks 11 and 12)
- 4. The number of participants achieving BP control (≤135/85 mmHg; week 12)
- 5. Use and acceptability of the SaltSwitch app and salt substitute at week 12 (intervention group only)

Serious adverse events will also be recorded during the trial period. If the intervention is found to be effective cost-effectiveness and cost-utility analyses will also be conducted.

Statistical Methods

Study power

A total of 326 participants (163 per group) will provide 80% power at a 5% level of significance (two-sided) to detect a minimum effect size of 0.33 standard deviation (SD) in the primary outcome measure between groups at week 12 allowing for 10% loss to follow-up. This effect size is based on the SD derived from the SaltSwitch pilot study data (1400mg/day) where estimations of 24hr urinary sodium excretion were calculated using spot urine samples and a standard urine volume of 1.99L.

Statistical analysis

[figure not shown]
The primary outcome will be analysed using linear regression model adjusting for baseline outcome value and stratification factors. Model-adjusted mean differences between two groups will be estimated with 95% confidence interval and p-value. Multiple imputation will be used on missing primary outcome data in the primary intention to treat (ITT) analysis; this method creates multiple imputed datasets for incomplete outcome variables that are analysed using same regression models and combined for one inference. The Markov chain Monte Carlo method will be used to produce the parameter estimates, assuming the data

Not for Public Circulation or Reproduction

are from a multivariate normal distribution and are missing at random. Sensitivity analyses using different assumptions on the missing data, e.g. complete case analysis and last value carried forward, will also be considered to test the robustness of main trial analysis. Per protocol analysis will be performed for participants with no major protocol violations. Generalised linear regression models will be used to analyse secondary outcomes, using a link function appropriate to the distribution of outcome variable. Like the primary outcome analysis, the regression model will adjust for baseline outcome value and stratification factors where appropriate. Model-adjusted group differences will be presented with 95% confidence intervals and p-values. For the primary and key secondary outcomes, the heterogeneity of treatment effects between Māori and non-Māori participants will be tested using an interaction term between treatment group and ethnicity in the main model, and also for participants in two different age groups (<55yrs and 55yrs+). If the intervention is found to be effective, cost-effectiveness and cost-utility analyses will be pre-specified in a separate economic analysis plan and conducted by an Economist at the University of Otago Wellington.

Not for Public Circulation or Reproduction

2. Study Plan Schematic

Not for Public Circulation or Reproduction

3. Background and rationale

High blood pressure (BP) is the leading cause of premature and preventable death worldwide¹, with the number affected projected to rise from ~0.9 billion in 2000 to ~1.6 billion by 2025². High BP is also a major risk factor for cardiovascular disease (CVD)³, which in turn is responsible for approximately one third of all deaths in countries belonging to the Organization for Economic Cooperation and Development (OECD) ⁴.

The relationship between high BP and dietary sodium intake is widely recognised⁵ with long-term dietary sodium reduction resulting in a fall in BP for both hypertensive and normotensive individuals, regardless of sex, ethnic group⁶⁻⁸ or use of BP lowering medication⁹. While larger reductions in dietary sodium are related to larger falls in BP, even modest reductions can reduce BP and the associated morbidity and mortality from CVD⁸.

However, most countries globally do not have Government-led salt reduction programs which encourage and enable widespread changes in the food environment¹⁰, and for those that do, the trajectory of change in population sodium intakes has been slow^{11, 12}. Therefore, effective, scalable dietary interventions to reduce the sodium intake of individuals are critical, particularly if OECD countries are to realize their 2025 commitment to The World Health Organization (WHO) to reduce population sodium intakes by 30% by 2025¹³.

Two promising approaches are mobile health (mHealth) interventions and dietary salt substitutes. Mobile phones and smartphones are becoming synonymous with personal health; global mobile phone ownership was predicted to be 67% in 2019¹⁴, with >90% ownership in most middle and high income countries where 70% or more own a smartphone¹⁵. A growing body of recent evidence also suggests electronic health and mHealth interventions can support dietary behavior change^{16, 17} and reduce BP^{17, 18}. However, there have been very few robust randomized controlled trials (RCTs) of app-based interventions for dietary sodium reduction or BP management^{18, 19}.

In 2014/15 we conducted a pilot trial of the potential six-week effects of the SaltSwitch smartphone app to support adults with diagnosed CVD to make lower sodium food choices²⁰. SaltSwitch targets sodium consumed from packaged foods, which contributes ~70% of the sodium (and thus salt) consumed in Western countries²¹. SaltSwitch is a feature within the FoodSwitch app; by selecting this feature users can scan the barcode of a packaged food using their phone camera and receive an immediate traffic light nutrition label alongside a list of healthier, lower sodium options to switch to (Figure 1). The findings of our pilot (n=66) supported a larger trial with longer term follow-up (mean (95% CI) reduction in household purchases of salt: 0.3 (0.58 to 0.03) g/MJ or ~0.7 g per person per day)²⁰.

However, SaltSwitch does not address discretionary salt added in cooking and at the table, which accounts for ~15% of dietary intakes (the remainder is found naturally in fresh foods)²¹; this need can be met with dietary salt substitutes, which are used in place of regular table salt. Dietary salt substitutes are gaining in popularity because they are higher in potassium and lower in sodium but have a similar taste and flavour, thus reducing BP without requiring a change to habitual discretionary 'salt' use. Dietary salt substitutes have been found to be acceptable and effective in reducing BP in China^{22, 23}, and evidence from a 2019 meta-analysis (n=21 RCTs) found using a salt substitute can lead to a significant reduction in systolic and diastolic BP (DBP) for both hypertensive and normotensive adults (overall reduction: -7.8 (-9.5 to -6.2) mm Hg and -4.0 (-5.2 to -2.7) mm Hg, respectively)²⁴. However, the overall quality of evidence in the 2019 review was considered low, and there were few studies (n=8/21) in high income countries where discretionary salt generally contributes a lower proportion of total salt intake (~15% vs. 76%²⁵)²¹. Nonetheless, salt substitutes hold promise for reducing sodium intakes because the population benefits far outweigh any risks²⁶, they are cheap, easy to use, include potassium, and act as a salient reminder of the importance of reducing dietary salt from all sources²⁷.

Not for Public Circulation or Reproduction

4. Objectives

The primary objective of this study is to determine the effects of a 12-week dietary salt reduction intervention (SaltSwitch app + dietary salt substitute) on urinary sodium excretion in adults with high BP.

The secondary objectives are to determine the effects of the dietary salt reduction intervention on: (1) urinary potassium excretion (week 12), (2) systolic blood pressure at week 12 (3) sodium content of packaged food purchases (weeks 11 & 12), (4) the number of participants achieving BP control (≤135/85 mmHg; week 12), and (5) use and acceptability of the SaltSwitch app and dietary salt substitute (week 12).

Additional objectives are to record serious adverse events, and if the intervention is found to be effective then cost-effectiveness and cost-utility analyses will also be completed.

4.1 Hypotheses

The primary hypothesis is that 12-weeks intervention with the dietary salt reduction intervention (SaltSwitch smartphone app + dietary salt substitute) will reduce the sodium intakes (measured using urinary sodium excretion) of adults with high BP, compared with control.

4.2 Secondary hypotheses

12-weeks intervention with the dietary salt reduction intervention (SaltSwitch smartphone app + dietary salt substitute) will, compared with control:

- Increase urinary potassium excretion
- Reduce systolic blood pressure
- Reduce the sodium content of packaged food purchases
- Result in a larger proportion of participants achieving BP control (≤135/85 mmHg)
- Be cost-effective

It is also anticipated that the SaltSwitch app and dietary salt substitute will be used frequently and be acceptable to participants.

Not for Public Circulation or Reproduction

5. Study Design

5.1 Inclusion criteria

Participants will be eligible if they:

- Are aged 18 years or older
- Own a smartphone (iPhone or Android)
- Have a seated SBP of 140-200 mmHg and/or diastolic BP (DBP) of 85-120 mmHg at screening
- Are willing to do grocery shopping during the study period
- Can read and understand English
- Can provide informed consent

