5.2 Exclusion criteria

Participants will be excluded if they:

- Currently use a dietary salt substitute
- Currently use the FoodSwitch app
- Have a contraindication to changing dietary sodium or potassium intake e.g. severe kidney disease or use a potassium sparing diuretic
- Are taking medication that may lead to hyponatraemia or acute build-up of body water such as furosemide, regular NSAID use, or regular prednisone use
- Have had a stroke or cardiovascular event (hospitalisation for heart attack, coronary artery revascularisation (CABG or stenting), stroke or heart failure) in the previous 6 months
- Have diagnosed heart failure

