5.3 Recruitment

Participants will be recruited using four main methods:

- (1) Face-to-face recruitment at Green Cross pharmacies, in shopping malls, at local events and markets, and in the Stroke Foundation blood pressure van.
- (2) Through Green Cross and other GP clinics/primary care providers that the researchers have existing relationships with e.g. The Fono
- (3) Using social media e.g. Facebook, where adverts will be targeted to the characteristics of the intended study population and information given to direct people to Green Cross pharmacies or their local health provider to have their BP taken or a screening clinic at The University of Auckland's Grafton Campus
- (4) Via market research panels where a survey is sent to the panel and those who are interested can complete some questions about their eligibility and supply contact details; they will then be invited to attend a screening clinic at Grafton Campus or directed to a Green Cross pharmacy or their local health provider to obtain BP measurements.

We will make every effort to employ Māori and Pacific Research Assistants (RAs) for recruitment of participants in shopping malls, and these same staff members will follow up participants by telephone throughout the study. Text messages inviting people registered with Green Cross for their prescriptions may also be used, and leaders of Māori communities NIHI has existing relationships with may be approached to increase recruitment of Māori. Recruitment will start in the Auckland region but may extend to other regions, if required to meet recruitment targets. Recruitment will be targeted to regions with higher proportions of Māori and low-income residents. Potential participants will watch a short study video and/or have the study explained to them either at the shopping mall, pharmacy or by their healthcare provider. A referral form will be completed where weight, BP, and smartphone ownership will be recorded. Interested people with a SBP

Not for Public Circulation or Reproduction

≥140mmHg and/or DBP≥85mmHg who own a smartphone (iPhone or Android) will provide a phone number and email address and consent to their details being forwarded to a study RA, who will call and administer a screening questionnaire to confirm eligibility.

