5.10 Participant screening

Potentially eligible participants will receive a follow up phone call from a study RA and a screening questionnaire will be administered. The screening questionnaire will collect date of birth and gender (male, female, gender diverse, prefer not to specify), and information on remaining inclusion/exclusion criteria relevant to the screening period: type of smartphone, contribution to household grocery shopping (or willing to for the study period), able to read and understand English, current use of a dietary salt substitute or the FoodSwitch app, contraindication to reducing salt or increasing potassium in their diet, recent stroke or cardiovascular event, or diagnosed heart failure. Eligible participants will be sent a text link to download the study smartphone app.

5.11 Changes to referral and screening process due to Covid-19 – Addition of remote screening option

Due to Covid-19 and closure of The University of Auckland campuses until the end of July, a remote referral and screening process has been devised to allow the study to continue during this period and ensure the safety of study participants and staff. This remote screening option will be offered to any participants recruited through self-referral methods such as market research surveys and Facebook who are not able to attend a clinic for screening measurements. Instead of attending a face to face clinic the participant will be screened over the phone and, if eligible,

Not for Public Circulation or Reproduction

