asked to self-report their weight and height. They may self-report these measures either by measuring them at home or by calling their GP if they have had a measure in the last three months. If they are unable to provide the measurements, they will be placed on hold until face to face clinics are deemed safe to proceed. If they can provide measurements, they will be couried a blood pressure monitor and guided over the phone by a Research Assistant to take three seated blood pressure measurements (one minute apart as per the protocol) and read these to the Research Assistant. The Research Assistant will then determine if the participant is eligible to proceed with the study based on the eligibility criteria and, if so, support the participant to progress to the consent and baseline phase of the study. If they are ineligible to proceed the Research Assistant will provide guidance on return of the blood pressure monitor. A flow diagram outlining the remote screening option process can be found in Appendix 5.

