Blood pressure will be collected by the participant on a home-based automated Wi-Fi enable BP monitor using methods adapted from the PATHWAY-2 trial and according to European Society of Cardiology guidelines^{31,32}. Participants will collect BP measures in triplicate after 5 mins rest, 1 minute apart. Measures will be taken both morning and evening, ideally at the same time each day during week -1 +/- two weeks). Participants will receive twice-daily notifications to their phone to remind them to collect their BP. If no BP measures have been received by researchers within one week of the phone call to confirm receipt of the monitor, reminder notifications will be sent and the participant will receive a phone call from a study RA to ensure they are confident in using the monitor. If less than six BP measures have been received within two weeks following courier of the BP monitor, BP data will be considered missing, the participant will be excluded, and the BP monitor will returned to researchers. Blood pressure measures will be received in real time directly from participant's monitors via an Application Programming Interface (API). Consistently elevated SBP (>180mmHg for three consecutive days including any missing days), consistently low SBP (<90mmHg for three consecutive days including any missing days), or major changes in SBP from baseline (>20mmHg) will trigger a notification to be sent to the study staff. The RA will confirm this by investigating the raw data and call the participant advising them that their BP measure is outside the normal range and it is recommended that they visit their GP as soon as possible. The RA will send a letter to notify a participant's GP where required.

Collection of barcodes for packaged food purchases

Participants will scan the barcode of all packaged foods and beverages bought into the home for their consumption during the two-week baseline period (weeks -2 and -1 +/- two weeks). Weekly notifications will be sent to their phone via the study smartphone app to remind them to complete the scanning. Barcodes will be used as unique product identifiers for linking with the Nutritrack supermarket food composition database[30] to determine the sodium content of food purchases. If no shopping purchase information has been returned for the baseline period, these data will be considered missing.

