Notification of randomisation (contact 3 – text message)

At the end of baseline (end of week -1), a study RA will confirm eligibility (minimum of six BP measures received, one urine sample, and 10 scanned food purchases) and text the participant (contact 3) to notify them of the group they have been allocated to. The RA will activate the participants study smartphone app to receive the appropriate notifications, based on their allocation. The RA will call participants in the intervention group to support them download the SaltSwitch smartphone app, enter a code to 'unlock' it, and watch a short tutorial (within the app) on how to use it. The intervention group will be notified that they will receive a supply of study salt in the mail.

Study end (contact 4 – a. Phone call and b. Email/Letter)

Participants will receive a notification via the study app at the end of week 12 to complete the follow-up questionnaire. If the follow up questionnaire has not been completed within one week following the end of the study, a follow-up phone call(s) (contact 4a.) may be required. On completion of the follow up questionnaire participants will receive a notification thanking them for their participation, a summary of their BP measures over the study, and more information about the dietary salt substitute. A study completion email or letter (contact 4b.) will also be sent to participants which will include instructions (1) to download the BlipCare smartphone app to monitor their BP measures post study-completion (2) to change the settings in their phone to enable them to continue using the SaltSwitch app but to cease collection of their use of the app by Google Analytics if in the intervention group (3) to download the SaltSwitch app (control group) and on how to purchase the dietary salt substitute. The RA will disconnect the participant's blood pressure monitor from the study system to stop data being sent to the study team.

Not for Public Circulation or Reproduction

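### The BP entry rule joins two bounded ranges with and/or, so a reading above one upper limit still qualifies through the other pressure

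*Protocol*

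**What the plan says.** Section 5.1 and the main inclusion criteria in the Overview give one BP criterion in the same words: "Have a seated SBP of 140-200 mmHg and/or diastolic BP (DBP) of 85-120 mmHg at screening".

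Other places that touch BP at or around entry:

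- **Overview, study population.** At least "80% will have a recorded systolic BP (SBP) of" 140 mmHg or more at screening.
- **Section 5.3, referral.** The step passes on people with SBP "≥140mmHg and/or DBP≥85mmHg who own a smartphone (iPhone or Android) will provide a phone number and email address". It has lower limits only.
- **Section 5.2, exclusions.** The list ends with "Have diagnosed heart failure" and contains no BP value.
- **Section 5.10, screening call.** It collects "information on remaining inclusion/exclusion criteria relevant to the screening period", and BP is not among the items then named. Table 1 (section 5.21) likewise puts BP in the first eligibility step, at referral, and not in the second. Appendix 2 says that the screening form covers the full list of criteria.
- **Section 5.11, remote screening.** The research assistant "will then determine if the participant is eligible to proceed with the study based on the eligibility criteria".
- **Section 5.20, check before randomisation.** It asks for a "minimum of six BP measures received, one urine sample, and 10 scanned food purchases", so it counts BP readings without looking at their level.
- **Section 5.13, home BP alerts.** Staff are notified of SBP above 180 mmHg or below 90 mmHg for three consecutive days, and "major changes in SBP from baseline (>20mmHg) will trigger a notification to be sent to the study staff".

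**The concern.** Upper limits of 200 and 120 mmHg have little evident purpose other than to keep people with very high BP out of a 12-week dietary trial. The *and/or* is needed for the lower limits, because the trial means to take people with raised diastolic pressure alone. The same *and/or* also governs the upper limits, however, and there it works against them: a person above one limit is let in by the other pressure.

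The rule also behaves perversely near its edges. Among people above one limit, a higher second pressure can turn a refusal into an acceptance.

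What is at stake is consistent and safe eligibility decisions. GPs, nurses, pharmacists and research assistants measure and refer at many venues, and section 11.1 requires the protocol to be conducted as described. Someone who admits a person at 210/100 is following the text; someone who refuses is departing from it.

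**Working it through.** No figure in the protocol is derived from this criterion, so there is none to reproduce. The sample size in section 6.1 rests on 0.33 SD in urinary sodium, 80% power and 10% loss, and uses no BP limit. The check is one of logic.

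**Inputs.** SBP range 140–200 and DBP range 85–120 mmHg (Overview and section 5.1); lower limits 140 and 85 (section 5.3); alert limits (section 5.13); 326 participants and the 80% expectation (Overview).

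**Two rules.**

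- As written: eligible if (140 ≤ SBP ≤ 200) or (85 ≤ DBP ≤ 120).
- Lower limits as alternatives, upper limits always applied: eligible if (SBP ≥ 140 or DBP ≥ 85) and SBP ≤ 200 and DBP ≤ 120.

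| SBP/DBP | SBP in range | DBP in range | As written | With true upper limits |
|---|---|---|---|---|
| 210/100 | no | yes | eligible | refused |
| 240/110 | no | yes | eligible | refused |
| 205/85 | no | yes | eligible | refused |
| 205/84 | no | no | refused | refused |
| 210/80 | no | no | refused | refused |
| 170/130 | yes | no | eligible | refused |
| 140/125 | yes | no | eligible | refused |
| 139/125 | no | no | refused | refused |
| 210/125 | no | no | refused | refused |
| 150/95 | yes | yes | eligible | eligible |
| 130/90 | no | yes | eligible | eligible |

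The perverse step shows in two pairs: 205/84 is refused and 205/85 admitted; 139/125 is refused and 140/125 admitted. Every pair in the table meets at least one lower limit, so the referral step in section 5.3 passes all of them.

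**Can *and/or* be read as *and*?** No. That reading would refuse 130/90, which section 5.3 refers because 90 ≥ 85. It would also leave the 80% expectation without a purpose, since everyone would then have SBP of at least 140. As the Overview stands, 0.80 × 326 = 260.8, so at least 261 have SBP of 140 or more and at most 326 − 261 = 65 have SBP below 140. The *or* is meant for the lower limits.

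**Does the corrected rule change anything else?** Suppose a pair meets the corrected rule. Either SBP ≥ 140, and with SBP ≤ 200 it is inside the systolic range; or DBP ≥ 85, and with DBP ≤ 120 it is inside the diastolic range. Either way the present rule admits it, so nobody is newly admitted. The only people removed have one pressure in range and the other above its upper limit.

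**Do the home alerts fill the gap?**

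- Home SBP staying at 210: 210 > 180, so three consecutive days trigger a notification.
- Home BP stable at 170/130: 170 is not above 180, not below 90, and the change from baseline is 0, not above 20. Nothing triggers, because every trigger is systolic.

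**The case against.** The strongest reply is that this is compact drafting whose intent is plain, that staff will treat 200 and 120 as ceilings anyway, and that safeguards exist. Much of this stands. Home readings arrive in real time from the baseline phase, so sustained SBP above 180 mmHg leads to a call, advice to see the GP and a letter where required (section 5.13). That covers the systolic examples if the home readings stay high. The principal investigator may withdraw a participant in their best interest (section 5.8), participants may stay on antihypertensive medication (section 5.7), and the protocol regards the app and salt substitute as low risk (section 8.3). But an alert or a later withdrawal does not bar entry, and a high DBP with stable SBP of 180 mmHg or less is not flagged. That staff probably know what was meant is a reason to write it down.

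A reader might go further in four ways that the protocol does not support:

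- *The upper limits do nothing.* They do refuse people when both pressures are out of range, such as 210/80 and 210/125.
- *Up to 65 participants may enter on DBP alone.* The 65 is the maximum with SBP below 140. A person at 210/100 also enters through DBP but counts towards the 80%. Nor does the 65 estimate how many exceed a limit.
- *The trial result is biased.* Entry is decided before randomisation and the rule is the same for both arms.
- *The protocol must add a diastolic alert.* The alerts matter here only because they do not replace an entry limit; whether to widen them is a separate clinical choice.

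**Conclusion.** The criterion is wrong as written. Followed literally, it admits people above one of its own upper limits whenever the other pressure is in range, and it refuses some people whose second pressure is lower. No other section sets an entry ceiling.

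The size is modest. Without a BP distribution in the protocol the number affected cannot be calculated; that it is small is a judgement. The sample size, outcomes and analysis do not change. Actual harm is not shown, and the purpose of the limits is inferred from their values, since the protocol does not state it. The conclusion about the wording needs neither assumption: it follows from the text alone. Because the rule bears on participant safety and the repair is nearly free, it should be corrected.

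**What to change.** In the Overview and section 5.1, replace the BP criterion with:

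> Seated SBP ≥140 mmHg and/or DBP ≥85 mmHg, with SBP ≤200 mmHg and DBP ≤120 mmHg.

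Add the same two upper limits to the referral step in section 5.3. Table 1 places the BP check at referral and section 5.3 has lower limits only, so rewording the criterion alone would leave that step without a ceiling, even though Appendix 2 says the screening form covers the full list. Section 5.11 refers back to the criteria and needs no change.

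The cost is one sentence reworded in two places and one short addition in a third. A few people with very high readings will no longer be enrolled.
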